## PROTOCOL SYNOPSIS

### Clinical Protocol ESR-14-10744

Study Title: WINDOW OF OPPORTUNITY PHASE II STUDY OF MEDI4736 OR MEDI4736 + TREMELIMUMAB IN SURGICALLY RESECTABLE MALIGNANT PLEURAL MESOTHELIOMA
Protocol Number: ESR-14-10744
Clinical Phase: II
Study Duration: 24 months
Investigational Product(s) and Reference Therapy: MEDI4736 will be supplied in glass vials containing 500 mg of liquid solution at a concentration of 50 mg/mL for intravenous (IV) administration.  Tremelimumab is supplied as a sterile IV solution in 20 mL clear glass vials with a rubber stopper and aluminum seal.
Research Hypothesis: Our hypothesis is that neoadjuvant therapy with anti-PD-L1 monoclonal antibody MEDI4736 in combination with anti-CTLA-4 monoclonal antibody tremelimumab will result in favorable alterations of the intratumoral immunologic environment in subjects undergoing resectional surgery for malignant pleural mesothelioma (MPM).
Objectives:  Primary Objectives: The primary objective of this study will be comparison of the ratio of intratumoral cytotoxic T cells to regulatory T cells (CD8/Treg) before and after treatment with combination MEDI-4736 and Tremelimumab checkpoint inhibitor therapy.  Secondary Objective(s): The secondary objectives of this study are: 

1) Comparison of the percentage of inducible T-cell co-stimulator (ICOS) positive intratumoral CD4 T cells before and after treatment with combination MEDI-4736 and Tremelimumab checkpoint inhibitor therapy.

2) Comparison of tumor tissue expression (Ventana assay) of programmed death-ligand 1 (PD-L1) before and after treatment with combination MEDI-4736 and Tremelimumab checkpoint inhibitor therapy.

- 3) Comparison of the ratio of the intratumoral CD8/Treg ratio in patients treated with combination therapy (MEDI-4736 and Tremelimumab) compared to either patients treated with MEDI-4736 alone, and separately compare to untreated patients.
- 4) Comparison of the percentage of inducible T-cell co-stimulator (ICOS) positive intratumoral CD4 T cells in patients treated with combination therapy (MEDI-4736 and Tremelimumab) compared to either patients treated with MEDI-4736 alone, and separately compare to untreated patients.
- 5) Comparison of tumor tissue expression (Ventana assay) of programmed death-ligand 1 (PD-L1) in patients treated with combination therapy (MEDI-4736 and Tremelimumab) compared to either patients treated with MEDI-4736 alone, and separately compare to untreated patients.
- 6) Comparison of overall survival in patients treated with either MEDI-4736 alone or MEDI-4736 plus Tremelimumab with historical untreated controls. These analysis will be post-protocol analysis based upon data obtained from the standard of care follow up in our post-surgical patients.
- 7) Comparison of recurrence-free survival in patients treated with either MEDI-4736 alone or MEDI-4736 plus Tremelimumab with historical untreated controls. These analysis will be post-protocol analysis based upon data obtained from the standard of care follow up in our post-surgical patients.

#### **Study Design:**

Subjects with MPM will undergo surgical mediastinal lymph node biopsy (cervical mediastinoscopy) and simultaneous surgical biopsy of the pleural tumor by thoracoscopy, at which time tumor tissue (at least 2 g) and peripheral blood will be collected for the study. These procedures are performed as our standard of care in the treatment of these subjects. The subject will be randomized. Three days to three weeks after the biopsy, 20 evaluable subjects (if tissue obtained) will be randomly treated with either MEDI-4736 alone (15 mg/kg once intravenously) (n=8) or MEDI-4736 (1500 mg once intravenously) plus tremelimumab (75 mg once intravenously) (n=8), or a control group (n=4) in a randomized controlled study design. There will be two treatment arms (MEDI4736 only and combination MEDI4736+tremelimumab) and one untreated arm (control). Randomization, stratified by receiving previous chemotherapy or not, will be performed and will help to minimize patient selection biases between three arms. Subjects under 30 kg will be treated with weight-based dosing for both MEDI4736 and Tremelimumab combination therapy. These patients are excluded from fixed based dosing to limit endotoxin exposure from the drug preparations. One to six weeks after the infusion, subjects will undergo resectional surgery, including extrapleural pneumonectomy (EPP) or pleurectomy/decortication (P/D), at which time the tumor will be removed (typically 200-1000 g) and obtained for study. Four patients that do not undergo treatment with MEDI-4736 or tremelimumab will be included as controls. Blood will be obtained after the induction of general anesthesia for both the thoracoscopy procedure and the EPP or P/D resectional procedure, as is routinely done in these procedures. The sixth rib will be obtained at the time of the resection. After the removal of the tumor, our standard protocol includes intraoperative heated chemotherapy using a lavage of intracavitary cisplatin in the presence of conserved renal function (Sugarbaker et al., 2013, 2014; Richards et al., 2006).

Tumor tissues obtained either by thorascopic biopsy or by resectional surgery will be evaluated by time-of-flight mass spectrometry (CyTOF) to determine intratumoral CD8/Treg ratios and percentage of ICOS positive CD4 T cells, and by immunohistochemistry (Ventana assay) to determine the tissue expression of PD-L1. These variables will be compared before and after treatment (changes within the same patient tumor), or between treatment groups (MEDI-4736 alone, MEDI-4736+tremelimumab, untreated) following treatment. Additional hypothesis-generating analyses will include a comprehensive systems based evaluation of the intratumoral immune cell population composition and phenotype [e.g., dendritic cells, macrophages, myeloid derived suppressor cells (MDSC), neutrophils, T-cell subsets, natural killer (NK) cells, and B cells], and immune-related gene expression using the nanostring system within the tumors, blood, and bone marrow of patients in all treatment groups.

**Number of Centers:** 1

**Number of Subjects:** 20

**Study Population:**

Subjects aged 18 years or older with resectable MPM

**Inclusion Criteria:**

1. Written informed consent obtained from the subject prior to performing any protocol-related procedures, including screening evaluations
2. Age  $\geq$  18 years at time of study entry
3. Eastern Cooperative Oncology Group (ECOG) performance status of 0 or 1
4. Adequate normal organ and marrow function as defined below:
  - Hemoglobin  $\geq$  9.0 g/dL
  - Absolute neutrophil count (ANC)  $\geq 1.5 \times 10^9/L$  ( $\geq 1500$  per mm $^3$ )
  - Platelet count  $\geq 100 \times 10^9/L$  ( $\geq 100,000$  per mm $^3$ )
  - Serum bilirubin  $\leq 1.5 \times$  institutional upper limit of normal (ULN) AST  $< 3.0$
  - Creatinine clearance  $> 50$  mL/min
  - Aspartate transaminase (AST) and alanine transaminase (ALT)  $\leq 2.5 \times$  ULN ( $\leq 5 \times$  ULN if documented liver metastasis are present);
  - Serum creatinine  $\leq 2.0$  mg/dL or calculated creatinine clearance  $\geq 50$  mL/min as determined by the Cockcroft-Gault equation;

**Males:**

$$\text{Creatinine CL} = \frac{\text{Weight (kg)} \times (140 - \text{Age})}{72 \times \text{serum creatinine (mg/dL)}}$$

**Females:**

$$\text{Creatinine CL} = \frac{\text{Weight (kg)} \times (140 - \text{Age})}{72 \times \text{serum creatinine (mg/dL)}} \times 0.85$$

5. Female subjects must either be of non-reproductive potential (i.e., post-menopausal by history:  $\geq 60$  years old and no menses for  $\geq 1$  year without an alternative medical cause; OR history of hysterectomy, OR history of bilateral tubal ligation, OR history of bilateral oophorectomy) or must have a negative serum pregnancy test upon study entry.
6. Subject is willing and able to comply with the protocol for the duration of the study including undergoing treatment and scheduled visits and examinations including follow up.
7. Surgically resectable MPM with no disease extension beyond the ipsilateral hemithorax
8. Planned resectional surgery for MPM [extrapleural pneumonectomy (EPP) or pleurectomy and decortication (P/D)]
9. Any MPM histology (epithelial, mixed, sarcomatoid)
  - a. N0 or N1 nodal disease, as present on preoperative chest CT and/or PET/CT
  - b. N2 nodal disease if no progression after 2 cycles of standard chemotherapy. Progression will be considered if additional N1 or N2 disease develop during chemotherapy.

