**Study Assessments and Criteria for Evaluation:**

**Safety Assessments:**

On the infusion day with MEDI4736 or MEDI4736 + tremelimumab, we will conduct clinical chemistry, hematology, and vitals. Subjects will be followed for 90 days after the last dose for safety to monitor any AEs, SAEs, etc.

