**Schedule of study assessments: Screening and Treatment Period (24 months: maximum of 1 dose)**

Visit	Screening (Up to 28 days before or on Day 1)				Oncology Visit	Infusion (3 days-3 weeks after mediastinoscopy & thoracoscopy)	Clinic Visit	Surgical Resection 1-6 weeks after infusion i	All assessments to be performed pre-infusion unless stated otherwise	
		Baseline	Mediastinoscopy & Thoracoscopy						Follow-up (after expected average 2 week hospital stay)	
Day	-28 to 1	1								
Week	-4 to 1	0	0-1	0-3	0-3		1-6	1-6	After discharge from hospital 1 week later, then 2 weeks later, then 4 weeks later. (±7 days)	
Recent formalin-fixed tumor biopsy for PD-L1 assay, if applicable										
Formal verification of eligibility criteria			X h							
Medical and surgical history	X									
Hepatitis B and C; HIV	X									
Urine hCG or serum βhCG a	X					As clinically indicated				
MEDI4736 administration						X (or MEDI473 + tremelimumab)				
MEDI4736 + tremelimumab						X (or MEDI4736)				
Physical examination b	X	X					X		X	
Vital signs (pre-during and post-infusion vital signs assessments) c	X	X				X				

Clinical Study Protocol

Drug Substance Tremelimumab

Study Number ESR-14-10744

Edition Number 8

Date 17 April 2019

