## **6. RESTRICTIONS DURING THE STUDY AND CONCOMITANT TREATMENT(S)**

### **6.1 Restrictions during the study**

#### **Contraception**

Female subjects of childbearing potential who are sexually active with a non-sterilized male partner must use at least one highly effective method of contraception (Table 5) from the time of screening and must agree to continue using such precautions for 90 days after the last dose of mono-therapy MEDI4736 or for 180 days after last dose of combination therapy with MEDI4736 and tremelimumab. The male partner of a female subject must also use male condom plus spermicide throughout this period. Cessation of birth control after this point should be discussed with a responsible physician. Not engaging in sexual activity is an acceptable practice; however, occasional abstinence, the rhythm method, and the withdrawal method are not acceptable methods of contraception. Female patients should refrain from breastfeeding and egg cell donation throughout this period.

- Females of childbearing potential are defined as those who are not surgically sterile (i.e., bilateral tubal ligation, bilateral oophorectomy, or complete hysterectomy) or postmenopausal (defined as 12 months with no menses without an alternative medical cause).
- Effective methods (including highly effective methods) of contraception are described in Table 5. A highly effective method of contraception is defined as one that results in a low failure rate (ie, less than 1% per year) when used consistently and correctly. Note that not all methods in Table 1 are considered highly effective.
- Non-sterilized male subjects who are sexually active with a female partner of childbearing potential must use male condom plus spermicide (see Table 5) from screening through 90 days after the last dose of mono-therapy MEDI4736 or for 180 days after last dose of combination therapy with MEDI4736 and tremelimumab. Not engaging in sexual activity is an acceptable practice; however, occasional abstinence, the rhythm method, and the withdrawal method are not acceptable methods of contraception. Male patients should refrain from sperm donation throughout this period. Female partners of a male subject must use an effective method of contraception throughout this period.

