### **7.1.1 Screening Phase**

Screening procedures will be performed up to 28 days before or on Day 1, unless otherwise specified. All subjects must first read, understand, and sign the IRB/REB/IEC-approved ICF before any study-specific screening procedures are performed. After signing the ICF, completing all screening procedures, and being deemed eligible for entry, subjects will be enrolled in the study. Procedures that are performed prior to the signing of the ICF and are considered standard of care may be used as screening assessments if they fall within the 28-day screening window.

All subjects who screen for this study will have a clinical diagnosis of MPM (based upon CT, and/or PET-CT, and or MRI radiographic findings) but not all subjects will have had this diagnosis confirmed by a tissue biopsy. In either case patients undergo thoracoscopy to assess resectability of disease, and to obtain tissue or additional tissue, when necessary, for diagnosis. Thoracoscopy will be performed in these subjects after signing the ICF.

The following procedures will be performed during the Screening Visit:

- Informed Consent
- Review of eligibility criteria
- Medical history and demographics
- Complete physical exam
- ECOG Performance Status
- Vitals signs, weight and height
- Review of prior/concomitant medications

- Imaging by CT/MRI, if applicable to study
- Clinical laboratory tests for:
  - Hematology (see Table 6)
  - Clinical chemistry (see Table 7)
  - TSH
  - Coagulation (PT, PTT, INR)
  - Creatinine Clearance
  - Serum pregnancy test (for women of childbearing potential only)
  - Hepatitis serologies
  - Urinalysis (see Table 8)
  - Disease-specific tumor markers

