### **7.1.2 Treatment Phase**

Procedures to be conducted during the treatment phase of the study are presented in the Schedule of Assessments.

Following the Screening Phase, subjects with MPM who are enrolled in the study will undergo surgical mediastinal lymph node biopsy (cervical mediastinoscopy) to evaluate nodal status and simultaneous surgical biopsy of the pleural tumor by thoracoscopy under general anesthesia, at which time tumor tissue (at least 2 g) and peripheral blood (25ml) will be collected for the study. These procedures are performed as our standard of care in the treatment of these subjects. The thoracoscopy procedure is part of our standard of care in both in subjects who have had a previous tissue biopsy and those who have not had a previous biopsy. It is performed to determine resectability of the tumor and to obtain tissue to confirm tissue diagnosis. In subjects who are consented to the study who have a suspected (clinical) diagnosis of MPM but not a tissue diagnosis, if the thoracoscopy procedure reveals that the subject does not have MPM, then these subjects will be removed from the study and their tissue and blood samples will be destroyed. These subjects will be replaced in the study.

Three days to three weeks later subjects will be treated with either MEDI4736 (15 mg/kg once intravenously) or MEDI4736 (1500 mg once intravenously) + tremelimumab (75 mg once intravenously). Subjects under 30 kg will be treated with weight-based dosing for both MEDI4736 and Tremelimumab combination therapy. These patients are excluded from fixed based dosing to limit endotoxin exposure from the drug preparations. A control group will include patients who are not treated with MEDI4736 or Tremelimumab. One to six weeks after treatment, subjects will undergo resectional surgery including extrapleural pneumonectomy or pleurectomy/decortication under general anesthesia, at which time the

Clinical Study Protocol

Drug Substance Tremelimumab

Study Number **ESR-14-10744**

Edition Number 8

Date 17 April 2019

tumor will be removed (typically 200-1000g) and obtained for study. Blood (25ml) also will be obtained for the study. The sixth rib will be obtained at the time of the resectional procedure as part of the routine procedure. After the removal of the tumor, our standard protocol (in the presence of conserved renal function) includes intraoperative heated chemotherapy using a lavage of intracavitary cisplatin.

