### **7.2.2 Clinical laboratory tests**

The following clinical laboratory tests will be performed (see the Schedule of Assessments, Appendix B for the timepoints of each test):

- Coagulation parameters: Activated partial thromboplastin time and International normalized ratio to be assessed at baseline and as clinically indicated
- Pregnancy test (female subjects of childbearing potential only)
  - Urine human chorionic gonadotropin
  - Serum beta-human chorionic gonadotropin (at screening only)
- Thyroid Stimulating Hormone

Clinical Study Protocol  
Drug Substance Tremelimumab  
Study Number **ESR-14-10744**  
Edition Number 8  
Date 17 April 2019

- free T3 and free T4 only if TSH is abnormal
- Other laboratory tests
  - Hepatitis A antibody, hepatitis B surface antigen, hepatitis C antibody
  - HIV antibody

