## APPENDIX B

### Schedule of study procedures: follow-up for subjects who have completed MEDI4736 or MEDI4736 plus Tremelimumab but did not have resection.

Evaluation	Time Since Last Dose of MEDI4736							
	Day ( $\pm 3$ )	Months ( $\pm 1$ week)						12 Months and Every 6 Months ( $\pm 2$ weeks)
	30	2	3	4	6	8	10	
Physical examination a	X							
Vital signs (temperature, respiratory rate, blood pressure, pulse)	X							
Weight	X							
Urine hCG or serum $\beta$ hCG	X							
AE/SAE assessment	X	X	X					
Concomitant medications	X	X	X					
Palliative radiotherapy	As clinically indicated							
<<World Health Organization>> <<ECOG>> performance status	X	X	X		X (and month 9)			X
Subsequent anti-cancer therapy	X	X	X	X	X	X	X	
Survival status: phone contact with subjects who refuse to return for evaluations and agree to be contacted		X	X	X	X	X	X	X (every 2 months)
Hematology	X	X	X					X
Serum chemistry	X	X	X					
Thyroid function tests (TSH, and fT3 and fT4) b	X							

a Full physical exam

b Free T3 and free T4 will only be measured if TSH is abnormal. They should also be measured if there is clinical suspicion of an adverse event related to the endocrine system.

c For patient questionnaires different approaches based on indication and study design

Clinical Study Protocol

Drug Substance Tremelimumab

Study Number **ESR-14-10744**

Edition Number 8

Date 17 April 2019

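### No pregnancy test is required between screening and the single infusion, so the last required result can be 4 to 7 weeks old at dosing

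*Combined protocol and SAP*

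**What the plan says.** **Entry.** Inclusion criterion 5 (Synopsis and Section 4.1) exempts women of non-reproductive potential. Any other woman "must have a negative serum pregnancy test upon study entry". Section 7.1.1 lists a serum pregnancy test at the Screening Visit. It also lets standard-of-care procedures done before consent count: they "may be used as screening assessments if they fall within the 28-day screening window".

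**Schedule of study assessments.** The row "Urine hCG or serum βhCG" is marked at Screening, which runs up to 28 days before Day 1 or on it. After that the row carries only an entry for testing when clinically indicated.

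**Infusion.** Section 7.1.2 puts dosing after the biopsy: "Three days to three weeks later subjects will be treated with either MEDI4736" alone or with tremelimumab. For the infusion day, the Synopsis (Safety Assessments) states that "we will conduct clinical chemistry, hematology, and vitals". No pregnancy test is listed.

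**Section 7.2.2.** Serum hCG is limited to screening. Urine hCG is listed without a time of its own, and the reader is told to "see the Schedule of Assessments, Appendix B for the timepoints of each test".

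**Appendix B.** This covers "follow-up for subjects who have completed MEDI4736 or MEDI4736 plus Tremelimumab but did not have resection". Its one hCG entry is at Day 30 after the last dose.

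**Safeguards.** Under Section 6.1, a sexually active woman of childbearing potential with a non-sterilized partner "must use at least one highly effective method of contraception (Table 5) from the time of screening". Exclusion 20 bars pregnant women, and Section 4.3 item 3 makes pregnancy a reason to give no further product.

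**The concern.** Each treated subject receives one dose (Section 5.6). A rule that stops further product once pregnancy is known can therefore protect only if pregnancy is known before that dose. The mandatory test is tied to study entry rather than to dosing, and a surgical biopsy and a wait of up to three weeks come between. The protocol itself treats exposure in pregnancy as a serious matter: contraception continues for 90 or 180 days after dosing (Section 6.1), and pregnancies are reported within 24 hours (Section 9.3.4.3). What is at stake is avoidable fetal exposure to one or two investigational antibodies. This is a patient-safety point confined to the two treated arms. It does not bear on the CD8/Treg comparison.

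**Working it through.** **Step 1. Is any test required between screening and infusion?**

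| Place | Test | Time | Mandatory before the dose? |
|---|---|---|---|
| Inclusion 5 (Synopsis, 4.1) | Serum | Study entry | Yes, at entry only |
| Section 7.1.1 | Serum | Screening Visit | Yes, at screening only |
| Schedule, hCG row | Urine or serum | Screening, then discretionary | Screening only |
| Synopsis, Safety Assessments | None listed | Infusion day | No |
| Section 7.2.2 | Serum; urine | Serum at screening; urine untimed | No further time given |
| Schedule, footnote j | None listed | When the pathology report arrives | No |
| Appendix B | Urine or serum | Day 30 after last dose, unresected subjects | No, post-dose |

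Section 7.2.2 sends the reader to the Schedule and Appendix B, and neither sets a mandatory pre-dose time after screening.

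**Step 2. How old can the last required result be at infusion?** The plan gives no figure to reproduce, so this is calendar arithmetic on its own windows.

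Inputs: screening up to 28 days before Day 1 (Schedule; Section 7.1.1); biopsy in weeks 0 to 1 and infusion in weeks 0 to 3 (Schedule, Week row); infusion 3 days to 3 weeks after biopsy (Schedule; Section 7.1.2).

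Maximum age = screening window + longest time from Day 1 to infusion.

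The documents leave Day 1 open. Footnote d links the Day 1 ECG to the start of infusion. The schedule's columns instead make Day 1 a separate Baseline visit placed before the biopsy.

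- Day 1 is the infusion day: 28 + 0 = 28 days (4.0 weeks).
- Day 1 is Baseline, infusion kept within the Week row: 28 + 21 = 49 days (7.0 weeks).
- Day 1 is Baseline, biopsy at the end of week 1 and infusion a full 3 weeks later: 28 + 7 + 21 = 56 days (8.0 weeks). This puts the infusion 28 days after Baseline, past the 21 days that the Week row allows.

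**Step 3. Scale.** Planned treated subjects: 8 + 8 = 16, plus any replacements. The number of childbearing potential is not given. For a deliberately high count, assume all 16. Section 6.1 defines a highly effective method as one failing in less than 1% per year with consistent and correct use. Taking 1% spread evenly over the year:

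- 28 days: 16 × 0.01 × 28/365 = 0.012 pregnancies
- 49 days: 16 × 0.01 × 49/365 = 0.021
- 56 days: 16 × 0.01 × 56/365 = 0.025

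This assumes correct contraception throughout the interval and leaves out a conception just before the entry test that is too early to detect. It shows the order of size only.

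**The case against.** **The risk is already very small.** Step 3 gives about 0.01 to 0.02 expected pregnancies on the 28- and 49-day readings, even with every treated subject counted. Women have also tested negative at entry, and exclusion 20 applies. This stands, and it limits the weight of the point. It does not supply a check of status before the only dose.

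**The text can be read as allowing for a later test.** Section 7.2.2 restricts serum hCG to screening but not urine hCG, which suggests that later urine testing was contemplated. Footnote e speaks generally of repeating screening laboratory tests at Day 1 unless done within the previous 3 days, and Section 7.1.1 groups the pregnancy test with the laboratory tests. A careful site might retest on that basis. But footnote e is attached to the chemistry and hematology rows. Some other footnote letters in the schedule are misplaced (formal eligibility verification carries the coagulation letter), so the attachment cannot settle the question either way. What is left is an ambiguity that a site may resolve without a test.

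**The ages are maxima.** A site that screens late in the window will hold a more recent result. This is correct, and the figures above are upper limits only.

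**Inferences the documents do not support.**

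- A reader might infer that the schedule puts the discretionary entry in the infusion column itself. The extracted table is broken, and the same words in the coagulation row fall under a different visit. The entry more likely spans all visits after screening.
- A reader might infer that the differing definitions of childbearing potential should be aligned to Section 6.1. Inclusion 5 counts a woman as post-menopausal by history only at 60 or over with at least a year without menses; Section 6.1 has no age floor. Aligning to Section 6.1 would remove the entry test for some women under 60, the opposite of what is wanted.

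**Conclusion.** The point holds as a cheap improvement to patient safety. Followed to the letter, the protocol permits the single dose on a pregnancy result up to 28 days old if Day 1 is the infusion day, or up to 49 days old by the schedule's Week row. A reader might take 8 weeks as the headline, but that requires adding the biopsy and infusion windows beyond the schedule's own limit for the infusion.

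A reader might also infer that pregnant women are likely to be dosed. The documents do not support that: the number of women of childbearing potential is unknown, the number affected may be zero, and the expected number is very small under the required contraception. The conclusion that no test is mandated before the dose is firm. The exact age depends on how Day 1 is read, and the scale figure depends on the assumptions in Step 3. Endpoints, alpha and power are unaffected.

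**What to change.** Require a urine hCG on the day of infusion, negative before dosing, for women of childbearing potential in both treated arms. If it is positive, do not dose; confirm by serum. State this in three places:

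1. The schedule's hCG row, as a required assessment at the infusion visit, keeping discretionary testing at other times.
2. The infusion-day list in the Synopsis (Safety Assessments).
3. Section 7.2.2, beside the urine hCG entry.

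Define the tested group as every woman who does not meet inclusion 5's description of non-reproductive potential, so that footnote a and Section 6.1 do not narrow it. Leave inclusion 5 as it stands.

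The cost is one amendment with three short text changes and one urine test for some of the 16 planned treated subjects, at a visit that already includes laboratory work. A positive result brings a short delay for confirmation. No visit is added, and sample size and analysis do not change. The required result would then be from the day of dosing, instead of up to 28 or 49 days old.
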